6.3 Blinding

Blinding

Given the pragmatic design, participants and treating providers will not be blinded to the care pathway. **Table 6** below summarizes blinding status for various study team members and also treating providers. Treating providers delivering the clinical pathways at a clinic and the Veteran patients in that pathway have no knowledge or training on the comparison pathway being delivered at other clinics as part of this study. Treating providers entering health factor data in the EHR will not be blinded. However, survey outcome assessors (RA conducting telephone

surveys) will be blinded to care pathway received. Study statisticians cannot be blinded to clinic randomization arm as they will be monitoring data collected in the EHR to track study flow, provide feedback to clinics and identify barriers or problems. Because the data entered in the EHR is different due to the nature of each of the interventions, it is not possible for study statisticians to be blinded in the conduct of this study. Study statisticians will be generating the randomization tables using a covariate constrained randomization and provide a report to inform clinics of their randomization arm.

Table 6. Blinding Summary for AIM-Back Trial

Study personnel	Clinic level randomization blinding status	Clinic level blinding status justification	Individual patient level data access	Individual patient level data access notes
PIs	Unblinded	Site recruitment and engagement role, troubleshooting barriers to clinical intervention delivery of programs; management of centralized intervention delivery	No	Access to aggregated patient data presented in reports for tracking and troubleshooting
Research coordinator	Unblinded	Site recruitment and engagement and monitoring of delivery of clinical intervention	No	Access to aggregated patient data presented in reports for tracking and troubleshooting
VA research assistant	Blinded		Yes	Administering patient surveys
DCRI research assistants	Blinded		Yes	Administering patient surveys
PhD Statistician	Unblinded	Involved in monitoring data in EHR including assessing targeted sample size goals; conducting and verifying covariate constrained randomization	Yes	Access intermittently to troubleshoot any problems with recruitment, data collection and data quality

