9.2 Sample Size and Randomization

In **Table 8** below we present a range of minimum detectable effect size differences for the primary outcomes of Pain Interference or Function Scores for both the administrative sample (N=84 per clinic) and survey sample (N=42 per clinic) for 16 clinics (8 clinics randomized to each arm) for Aim 1. Sample size calculations for the cluster randomized design were based on the net difference between the two conditions across baseline and 3-months follow-up.⁵⁰ We assumed over time correlations of 0.50 for both patients (based on data from the [name] et al. pilot study³³ and summary data available for Durham VA clinics, intraclass correlation coefficients (ICC) of 0.01, 0.02, and 0.05 to account for clinic clustering, and also adjusted for the potential group-level randomization of up to 4 stratification variables as baseline covariate adjustments where we conservatively assumed no reduction in either group or subject level variance components. For all calculations, the type-I error is 2.5% to account for the multiple primary outcomes and power is conservatively assumed to be 90% to guard against deviations from assumptions. The number needed at baseline (N_b) is based on an attrition rate of 20%. Note in the **below Table 4** that the scenarios above lead to having adequate power to detect a medium effect size for the primary outcomes for both the administrative and survey samples.

Table 8. Minimum detectable effect size differences for 90% power, alpha of 0.025 and ICC of 0.01, 0.02, and 0.05 for administrative outcome (n=84 per clinic) and survey outcome (n=42 per clinic)

Number of clinics per condition	Number of patients per clinic needed at post-intervention follow-up (Total N)	Minimum Detectable Effect Size Difference ICC=0.01	Minimum Detectable Effect Size Difference ICC=0.02	Minimum Detectable Effect Size Difference ICC=0.05	Number of patients per clinic needed at baseline with 20% attrition (Total N_b)
8	42 (N=672)	0.37	0.42	0.55	53 (N_b =848)
8	84 (N=1344)	0.30	0.36	0.50	105 (N_b =1680)

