9.3 Definition of Populations

As this is an embedded pragmatic trial, all adult subjects that present to clinics with LBP and are referred to one of the two arms of the trial with initial contact with pain navigator or central delivery for data collection will be eligible for the primary analysis as part of the administrative sample. A subset of these Veterans will be enrolled as research subjects so that more detailed research data can be collected at regular intervals for follow up. For this subgroup, equivalent numbers of Veterans with LBP will be enrolled at each clinic.

The primary analyses will be conducted on an intention-to-treat basis; patients will be analyzed in the group to which they were randomized, regardless of intervention adherence, using all available data. The main conclusions drawn from this trial will be based on the pre-specified hypotheses outlined below and will be tested with two-sided p-values at the standard 0.05 level, except where noted due to multiple primary outcomes. For all study outcomes, we will interpret differences between groups over time with reference to prior literature regarding clinically meaningful changes. Results from exploratory analyses will be interpreted with appropriate consideration for their exploratory nature. Statistical analyses will be performed using the latest release of SAS for Windows (Cary, NC) and R software.

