9.6 Data Analyses

Aim 1 Analyses

The primary outcomes are continuous and will be ascertained at the planned baseline and follow-up assessment (3 months) from administrative data collected from the EHR on all eligible LBP Veterans presenting at participating clinics. Changes in pain interference and/or physical function scores will be estimated and the primary hypotheses tested via hierarchical linear mixed-effects models with patients nested within clinics and baseline and 3 month values in the response vector.⁵⁵ Hierarchical linear models are a flexible and powerful analytic tool for clustered longitudinal continuous outcomes. The fixed-effect portion of the model will have the form: $Y_{ijk} = \beta_0 + \beta_1 * (followup) + \beta_2 * (followup * intervention)$ for clinic i , patient j , at time k . Random effects (clinics and time by clinics) will be included in the model to account for clustering of patients within clinics as the clinics are the unit of randomization, random effects will also be included to account for the within-patient correlation between repeated measures over time. We will assess the best fitting random effects structure by fitting a variety of random coefficient models (e.g., random intercept only, random intercept and linear slope) and assess using Akaike Information Criteria (AIC) model selection criteria.^{56,57} The predictors in the model will include a time effect and indicator variables for treatment interacting with the time effect. The intraclass correlation capturing the relationship of outcomes between patients seen at the same clinic is accounted for via the random effects for the clinics and time by clinics, which are assumed to be normally distributed. The model will be fit in the SAS procedure PROC MIXED using full likelihood approximation and the hypotheses will be tested by whether the estimated coefficient β_2 is positive and significantly different than 0 at the 0.025 level due to 2 primary outcome variables. We will include covariates used in the covariate constrained randomization⁴ (5 potential variables; average pain scores, clinic location (main medical center/community clinic), number of participating primary care providers, average level of opioid exposure of LBP patients at clinic, and average age of LBP patients at clinic) in our primary model as well as a limited number of patient-level covariates that are readily available in the EHR (age, gender, race and a comorbidity measure). While we have procedures in place to monitor timing of the 3-month follow-up assessment in the EHR, if we have a significant number of assessments outside the 1-month window for the 3-month assessment that are dropped from the primary analysis, we will conduct a sensitivity analysis including the assessments outside the window and estimating a 3-month treatment effect from this model.

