The survey outcomes for the enrolled subset of patients will be collected at baseline, 3, 6, 9, and 12 months and will include pain interference, function, intensity, catastrophizing, sleep, and depression (see Section 10 for full descriptions). These are all longitudinal continuous outcomes and a hierarchical linear model similar to that described for the primary aim will be fit. We will fit random coefficient models as described above (e.g. random intercept only, random intercept and linear slope) and assess using AIC model selection criteria to determine best model for the covariance structure. Similarly, we will determine the best model for the mean structure (e.g. linear, quadratic, dummy coding) as there are five outcome measurement occasions guided by descriptive plots and model fit assessed using AIC model selection criteria. Due to the timing of administration of baseline surveys that some baseline surveys may occur after the initial intervention contact, we will conduct sensitivity analysis treating baseline surveys after initial provider contact as occurring in the post-treatment period.

Aim 2 Analyses

As highlighted in the UG3 section we have strong clinical and scientific rationale to investigate chronic vs. acute LBP and previous opioid use vs. opioid naïve as *a priori* subgroups for treatment moderation.³⁸ We will define “chronic low back” as pain that has persisted for at least 3 months and resulted in pain on at least half the days in the past six months to be consistent with the NIH task force definition.⁴⁹ All participants will have chronicity of back pain assessed via the EHR template (see Section 6) at the time of initial referral to a given care pathway using questions specified in the NIH minimum dataset.⁴⁹ Opioid exposure prior to pathway entry will be defined as being prescribed at least one prescription opioid for 20 or more consecutive days (yes or no within 12 months prior to entering pathway).⁶⁴ This definition could be altered if different ones are suggested for use by the PMC3. These data will be obtained through VA’s Pharmacy Benefits Management System.

For the planned subgroup analyses for key moderators on the primary outcomes of pain interference and function will be the same modeling framework as described for AIM 1 with the addition of the indicator variable(s) for the moderator and associated interactions.⁶⁵ The fixed-effect portion of the model will have the form: $Y_{ijk} = \beta_0 +$

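### The AIC step for the primary model does not protect the time-by-clinic random effect; if it drops that term, type I error at the smaller planned ICCs rises to about 4.4–5.5% against a nominal 2.5%

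*Combined protocol and SAP*

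**What the plan says.** Section 9.6 (Aim 1 Analyses) describes a linear mixed model with baseline and 3-month values as responses. The treatment effect is beta_2, the follow-up-by-intervention coefficient. On clustering it says: "Random effects (clinics and time by clinics) will be included in the model to account for clustering of patients within clinics". It adds random effects for the correlation between a patient's repeated measures, and then says: "We will assess the best fitting random effects structure by fitting a variety of random coefficient models". The examples given are an intercept-only model and an intercept-plus-linear-slope model, compared by AIC. The level (patient or clinic) at which this choice operates is not stated. Two sentences later the text says again that the clinic and time-by-clinic effects account for the clinic correlation.

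The model is to be fitted in PROC MIXED by full likelihood. No denominator-df method is named. Each co-primary outcome is tested as "significantly different than 0 at the 0.025 level due to 2 primary outcome variables", and Section 9.3 makes the tests two-sided. The survey-outcome paragraph of the same section reuses the AIC procedure to choose the covariance structure. The sleep and moderator analyses also refer back to this modelling framework.

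**The concern.** Clinics are randomised, and beta_2 compares change over time between arms. Its clinic-level error is the variation between clinics in their change over time, which is the time-by-clinic variance. A clinic intercept does not capture that variation. If the time-by-clinic term is removed, beta_2 is tested essentially against patient-level error.

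In a cluster trial this term is required by the design, so goodness of fit should not decide whether it stays. With 16 clinics, AIC has little ability to detect a small but real variance component. An analyst who dropped the term because AIC preferred the intercept-only model could say that the plan had been followed. At stake is the 2.5% level set for each co-primary outcome to allow for there being two.

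**Working it through.** **Inputs**
- 8 clinics per arm and 84 patients per clinic at follow-up; ICC 0.01, 0.02, 0.05 (Section 9.2, Table 8).
- Error rate: "For all calculations, the type-I error is 2.5% to account for the multiple primary outcomes". Power is 90%.
- Over-time correlation 0.50 (Section 9.2). The sentence names only patients; the value for clinics is inferred in step 1.
- Clinic-level df: Table 8 agrees with the 5-df rows of Table 7 for 84 per clinic, so df = 2(8 − 1) − 5 = 9.
- Two occasions and full maximum likelihood (Section 9.6).

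**Step 1. Reproduce Table 8.** For the net difference in a cohort nested in clinics, with SD 1, g clinics per arm and m patients per clinic:

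MDE = (t[0.9875, 9] + t[0.90, 9]) × √{4[(1 − ICC)(1 − r_patient) + m·ICC·(1 − r_clinic)] / (m·g)}

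The t values are 2.685 + 1.383 = 4.068. With both correlations 0.5 and m = 84:

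| ICC | patient part | clinic part | clinic share | MDE | Table 8 |
|---|---|---|---|---|---|
| 0.01 | 0.495 | 0.420 | 46% | 0.300 | 0.30 |
| 0.02 | 0.490 | 0.840 | 63% | 0.362 | 0.36 |
| 0.05 | 0.475 | 2.100 | 82% | 0.504 | 0.50 |

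For example, at ICC 0.01: 4.068 × √(4 × 0.915 / 672) = 0.300. With r_clinic = 1 the clinic part vanishes and the MDE is about 0.22 at every ICC. The trial was therefore sized on time-by-clinic variance, which makes up 46–82% of the error variance in this formula.

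**Step 2. Simulate the null.** The stated model was fitted by full ML to 10,000 null trials per ICC, without covariates, with r = 0.5 at both levels and 84 per clinic. AIC drops the time-by-clinic variance (one parameter) when twice the log-likelihood gain is below 2. A kept model is tested with t(14), a reduced model with normal critical values.

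| ICC | dropped by AIC | error after AIC | error if always kept | error if always dropped |
|---|---|---|---|---|
| 0.01 | 54% | 5.3% | 2.7% | 8.8% |
| 0.02 | 19% | 5.0% | 3.5% | 16.6% |
| 0.05 | 0.9% | 3.6% | 3.5% | 31.2% |

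Smaller repeat simulations (1,500 to 2,500 runs) give these ranges when combined with the table:
- ICC 0.01: dropped 52–54%; error 4.9–5.4% after AIC, 2.5–2.7% if kept.
- ICC 0.02: dropped 18–21%; error 4.4–5.5% after AIC, 3.0–3.9% if kept.
- ICC 0.05: dropped about 1%; error 3.6–4.3% after AIC, 3.5–4.1% if kept.

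**Step 3. Vary the assumptions** (ICC 0.01 / 0.02 / 0.05 unless stated)
- t(9) when kept: 5.1 / 4.4 / 2.4% after AIC, against 2.0 / 2.5 / 2.3% always kept.
- Five clinic covariates, t(9): 5.8 / 4.8 / 3.5%, against 2.5 / 2.8 / 3.3%.
- Normal critical values throughout: 6.0 / 6.7 / 5.8%, against 4.8 / 5.8 / 5.8%. Most of the excess is then present before AIC acts.
- r_clinic = 1: 2.4–2.9% after AIC without covariates, 3.1–3.4% with five.
- r_clinic = 0.8, t(14): 5.4% against 2.9% at ICC 0.02, and 4.9% against 3.5% at ICC 0.05. The ICC at which AIC does harm depends on this unstated value.

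**The case against.** The strongest reply is that the plan already commits to the term. Section 9.6 names the time-by-clinic effect before and after the AIC sentence and again for Aim 2. The AIC sentence follows directly on the mention of within-patient correlation, so it can be read as tuning only the patient-level part. That reading is possible, and on it the inflation from dropping the term does not arise. It is not secured, however: the sentence refers to the random-effects structure without limit, and the survey paragraph reuses it for the covariance structure as a whole.

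A reader might infer that the patient-level reading is impossible because a patient slope cannot be estimated from two occasions. The documents do not support this. That count assumes an intercept–slope covariance, which the plan does not mention. With an uncorrelated intercept and slope plus a residual there are three parameters for three covariance elements, and the choice is a genuine one between equal and unequal variances at the two occasions.

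A reader might also infer that the selection could be steered, since "Study statisticians cannot be blinded to clinic randomization arm". AIC measures fit and does not reward a favourable arm effect, so that fact shows no added bias here.

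The remaining objections stand. The clinic correlation of 0.5 is inferred. The size depends on the ICC. With normal critical values the lack of a df rule matters more than AIC does.

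**Conclusion.** The point holds as an ambiguity in the primary analysis that should be closed. On one available reading, a stated rule can delete the term on which the test of beta_2 and the sample size both rest. Under that reading, with clinic over-time correlation 0.5 and t(14) or normal critical values as in step 2, type I error is about 5% at ICC 0.01 and 4.4–5.5% at ICC 0.02, against about 2.5% and 3–4% with the term always kept. At ICC 0.05 the addition is negligible, and with fully stable clinic effects there is little or none.

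A reader might conclude that the plan doubles the false-positive rate in general. The figures do not support that. Under the step 2 assumptions, doubling relative to the always-kept model appears only at ICC 0.01; at ICC 0.02 the ratio is about 1.4 to 1.5.

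Keeping the term is also not sufficient. With 16 clinics and normal critical values, error is about 4–6% even when it is kept. The simulations further assume equal clinic sizes, complete follow-up, normal data and, where covariates are included, covariates unrelated to outcome.

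**What to change.** Amend Section 9.6 in three respects:
1. State that clinic and time-by-clinic random effects stay in the primary model whatever the AIC and however small the estimated variance.
2. Confine any AIC choice to the patient-level covariance, or fix that as an unstructured 2×2 matrix and remove the AIC step.
3. Pre-specify the denominator df (clinic-based, or a small-sample correction), preferably with REML in place of full ML.

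Apply the same rule to the sleep, survey and moderator models that reuse this framework.

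The cost is wording only, with no change to design, recruitment or data. If the true time-by-clinic variance is zero, the test is slightly conservative: with r_clinic = 1, no covariates and t(14), the always-kept model rejects in about 1.0–1.3% of null trials instead of 2.5%. Table 8 already allows for a non-zero variance and 9 df, so the planned detectable effects are unaffected.

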
We have a solid plan for dropout of a clinic or low recruitment in block 1 that maintains the randomization and balance of covariates with the ability to add clinics to block 2 before the block 2 randomization.

To guard against drop out of clinics from block 2 we plan to add 2 reserve sites to the block 2 wave of randomization to use in case a clinic should drop out of block 2. We have adjusted the block sizes to have 10 clinics randomized in block 1 and have 8 clinics in block 2 (if no clinics drop out in block 1) which include 2 reserve clinics. Through the design process for this trial we have increased the number of clinics from 12 to 16 in part to provide a safeguard for the potential drop out of a clinic and still be able to conduct a successful trial (see Table 7 below that has effect sizes for 12 clinics with same number of patients per clinic as we targeting for 16 clinics and for 16 clinics with smaller number of patients per clinic).

Table 7. Sample Size Table for AIM-Back

Number of clinics per condition	Number of patients per clinic needed at post-intervention follow-up/ Total N	Df for baseline covariate adjustment	Minimum Detectable Difference (Effect size) ICC=0.01	Minimum Detectable Difference (Effect size) ICC=0.02	Minimum Detectable Difference (Effect size) ICC=0.05	Number needed at baseline with 20% attrition per clinic/ Total Nb
6	42/N=504	5	0.49	0.56	0.72	53/ Nb=636
		2	0.44	0.50	0.65	
6	84/N=1008	5	0.40	0.47	0.66	105/ Nb=1260
		2	0.35	0.42	0.59	
8	32/N=512	5	0.41	0.46	0.57	40/ Nb=640
		2	0.40	0.44	0.55	
8	63/N=1008	5	0.32	0.38	0.52	79/ Nb=1264
		2	0.31	0.37	0.50	
8	42/N=672	5	0.37	0.42	0.54	53/ Nb=848
		2	0.36	0.41	0.53	
8	84/N=1344	5	0.30	0.36	0.50	105/ Nb=1680
		2	0.29	0.35	0.49	

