$\beta_1^*(\text{moderator}) + \beta_2^*(\text{moderator}^*\text{intervention}) + \beta_3^*(\text{followup}) + \beta_4^*(\text{followup}^*\text{intervention}) + \beta_5^*(\text{moderator}^*\text{followup}) + \beta_6^*(\text{moderator}^*\text{intervention}^*\text{followup})$ for clinic i , patient j , at time k . A random effects (clinics and time by clinics) will be included in the model to account for clustering of patients within clinics, as the clinics are the unit of randomization. Differential change in pain interference or function by moderator for the two intervention groups is supported if the coefficient for β_6 is significantly different than zero at the $p=0.025$ level. For the adherence multinomial outcome, we will fit a generalized linear model with a random effect for clinic and cumulative logit link function. As the adherence outcome is potentially a 3-level outcome there will be two interaction terms to examine for moderation effects (e.g. whether the effect of the intervention by chronicity is different for those moderately adherent vs. not adherent and/or those fully adherent vs. not adherent).

Exploratory analyses to identify multidimensional subgroups from combinations of baseline characteristics (e.g. age, sex, opioid use) for treatment moderation of the primary outcomes of pain and function as well as per protocol adherence to treatment.

Patients are likely to vary in treatment response. This variation is known as heterogeneity of treatment effects (HTE). Exploration of HTE has typically focused on one-factor-at-a-time post-hoc subgroup analyses (as described in our planned subgroup analysis); however, it is possible to instead identify multidimensional subgroups exhibiting HTE. In particular, we will apply the data-driven method GUIDE⁶⁶(Generalized, Unbiased, Interaction Detection and Estimation) that can be used for longitudinal outcomes, so can incorporate all follow-up outcomes at 3 and 12-months, as well as multi-response outcomes. GUIDE uses a regression tree algorithm that identifies subgroups with heterogeneous effects and estimates how the treatment effect varies across the subgroups. We will include baseline demographic (e.g. age, sex, race) and clinical characteristics (e.g. LBP chronicity, opioid use, comorbid conditions) that are available from EHR. GUIDE provides bootstrap confidence intervals for the treatment effects of identified nodes and is available via a software package.

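### The primary test on 16 clinics uses full maximum likelihood, names no degrees-of-freedom method and does not protect the time-by-clinic effect from AIC, so its 0.025 level is not assured

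*Combined protocol and SAP*

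**What the plan says.** Section 9.6 (Aim 1 Analyses) tests each co-primary outcome through the follow-up-by-intervention coefficient, β2, at the 0.025 level. Section 9.3 makes p-values two-sided. On estimation: "The model will be fit in the SAS procedure PROC MIXED using full likelihood approximation". The Missing Data part of Section 9.6 likewise names maximum likelihood as the main technique for the primary outcomes.

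On clinic-level effects, Section 9.6 says "Random effects (clinics and time by clinics) will be included in the model to account for clustering of patients within clinics". It then says "We will assess the best fitting random effects structure by fitting a variety of random coefficient models (e.g., random intercept only", adds a random intercept and slope as a further candidate, and names AIC as the criterion. It does not say which level the search covers. The survey outcomes get the same treatment ("assess using AIC model selection criteria to determine best model for the covariance structure"). The moderator model again includes the clinic-level effects ("A random effects (clinics and time by clinics) will be included in the model to account for clustering of patients within clinics").

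No section names a df method or small-sample correction for β2. Df appear only in the sample-size work: Table 7 in Section 8 has a column headed "Df for baseline covariate adjustment", with values 5 and 2. Section 9.2 refers to "up to 4 stratification variables as baseline covariate adjustments where we conservatively assumed no reduction in either group or subject level variance components", whereas Section 9.6 lists five potential clinic covariates.

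**The concern.** Clinics are the unit of randomization, so the information about β2 comes from 16 clinics, not 1,344 patients. Three things then decide whether the test holds its level.

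- **Estimator.** ML makes no allowance for the fixed effects it estimates, so clinic-level variances come out too small. REML makes that allowance.
- **Reference distribution.** The two-sided 2.5% critical value is 2.24 (large-sample), 2.51 (14 df) or 2.69 (9 df). The same data can be significant under one and not another. What the software applies by default depends on how the model is coded, and the plan does not give the coding. The study statisticians are unblinded (Section 6.3), so this should not be left until data are in hand.
- **The error term.** The time-by-clinic variance is the clinic-level noise in the change that β2 measures. If AIC removes it, clustering of change is ignored.

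Splitting 5% across two primary outcomes protects the overall error only if each test really runs at 2.5%.

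**Working it through.** **Inputs.** Sections 9.2 and 9.6 and Tables 7 and 8 give g = 8 clinics per arm, m = 84 patients per clinic at follow-up (42 in the survey sample), ICC 0.01/0.02/0.05, over-time correlation 0.50, two-sided level 0.025 and power 90%. The 0.50 is stated for patients. Applying it to clinics as well is an assumption, and it reproduces the tables.

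**Step 1: the plan's own figures.** For a pre-post cohort design,

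MDE = (t₀.₉₈₇₅,df + t₀.₉₀,df) × √{4 × 0.5 × [(1 − ICC) + m·ICC] / (m·g)}.

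For m = 84 and ICC 0.01 the root is √{2 × (0.99 + 0.84)/672} = 0.0738. With df = 2(8 − 1) − 5 = 9, the quantiles sum to 2.685 + 1.383 = 4.068, so MDE = 0.300.

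| Reference (m = 84) | ICC 0.01 | 0.02 | 0.05 |
|---|---|---|---|
| Table 8, printed | 0.30 | 0.36 | 0.50 |
| 9 df | 0.300 | 0.362 | 0.504 |
| 10 df | 0.296 | 0.356 | 0.496 |
| 14 df | 0.284 | 0.343 | 0.477 |
| Normal | 0.260 | 0.313 | 0.436 |

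This row rules out the normal and 14-df references but does not separate 9 from 10 df. All 36 cells of Table 7 do. With df = 2(g − 1) minus the printed column, 31 cells match within 0.005 and all 36 within 0.01. Deducting one df fewer gives 20 and 28. Normal quantiles match none. The trial was therefore sized on a small-df clinic-level t test. The value 9 is inferred, not printed.

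**Step 2: size of the test as written.** Null trials were simulated with 16 clinics of 84 patients, the fixed effects of Section 9.6 and five non-prognostic clinic covariates as main effects, 100,000 trials per ICC. The Monte Carlo standard error is at most 0.08 points. Rejection rates in % (nominal 2.5):

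| Fit | Reference | ICC 0.01 | 0.02 | 0.05 |
|---|---|---|---|---|
| ML, term kept | 9 df | 2.3 | 2.9 | 3.2 |
| | 14 df | 3.3 | 4.0 | 4.4 |
| | large-sample | 5.6 | 6.4 | 6.9 |
| ML, AIC may drop term | 9 df | 3.0 | 3.5 | 3.2 |
| | 14 df | 4.2 | 4.7 | 4.4 |
| | large-sample | 6.8 | 7.3 | 7.0 |
| REML, term kept | 9 df | 1.5 | 1.8 | 1.9 |
| | 14 df | 2.3 | 2.6 | 2.7 |

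AIC dropped the term in 57%, 20% and 1% of trials at the three ICCs.

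**Step 3: replication.** A separate simulation (4,000 trials per setting, with no covariates or with five under constrained allocation) put ML at 1.8% to 7.7% across the same readings, and REML with the term kept at 2.1% to 2.9% on 14 df. A third (2,500 trials per ICC, term kept) gave ML 5.0–6.4% (large-sample), 2.8–3.8% (14 df) and 2.0–2.8% (9 df), and REML 1.9–2.4% on 14 df and about 1.8–2.2% with Kenward-Roger.

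**Step 4: both outcomes together.** Doubling the per-test rate gives an upper bound. With ML and the term kept, 9 df gives 2 × 2.3 = 4.6% to 2 × 3.2 = 6.4%. A large-sample reference gives 2 × 5.6 = 11.2% to 2 × 6.9 = 13.8%. If AIC may also drop the term, the latter reaches 2 × 7.3 = 14.6%.

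**The case against.** The strongest reply is that the high figures need unfavourable readings. The plan never states a large-sample reference, and its sample-size work points to a small-df t test. On that reading, with the term kept, ML gives 2.3% to 3.2%, close to nominal. This stands, and 7.3% is the worst corner rather than the expected error. But Section 9.6 does not carry the small df into the test, and ML with 14 df, also a natural choice, already gives 3.3% to 4.4%.

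Second, the AIC sentence follows the clause on within-patient correlation, and the text says before and after it that clinic and time-by-clinic effects are in the model. The search may be meant for the patient level only. That is a fair reading. The AIC step is also the smaller part: it adds 0.7, 0.6 and 0.0 points at 9 df. The finding does not depend on it.

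Third, doubling overstates the overall error when the two outcomes are correlated. If the test statistics correlate at 0.5 to 0.8 (an assumption; the plan gives no value), per-test rates of 5.6% to 7.3% give about 8.7% to 13.0% overall. This is still well above 5%. Relatedly, Section 9.6 asks for a positive β2, so false claims in that one direction are about half each two-sided rate. The ratio to nominal is unchanged.

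Finally, REML with Satterthwaite df and no standard-error adjustment gave 3.0% to 3.2%, no better than ML with 9 df. This limits which small-sample method to name, but it does not apply to fixed between-clinic df or Kenward-Roger.

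**Conclusion.** The concern holds. The plan specifies an estimator that understates clinic-level variance with 16 clinics, leaves the reference distribution open, and does not exempt the key random effect from model selection. Depending on how those gaps are filled, the nominal 2.5% test runs at about 2.3% to 7.3%. Most of the excess comes from ML combined with a large-sample reference. The level is not assured, but it is not always inflated.

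The result assumes a clinic-level over-time correlation of 0.5, complete follow-up at 84 per clinic, normally distributed effects, non-prognostic clinic covariates and no patient-level covariates. The sleep, morphine-equivalent, survey and moderator models were not simulated. The point should be fixed before outcome data are analysed, because it governs both co-primary tests.

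**What to change.** In Section 9.6:

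- Fit the primary model by REML.
- State that the clinic and time-by-clinic random effects remain whatever AIC shows, and limit any AIC choice to the patient-level covariance.
- Name the df method for β2. Between-clinic df of 16 − 2 = 14 suits clinic covariates entered as main effects, as Section 9.6 reads. The conservative choice matching Table 7 is 14 − 5 = 9. Kenward-Roger is an alternative.
- Apply the same rule to the sleep, morphine-equivalent, survey and moderator models.
- Reconcile the four covariates in Section 9.2 with the five in Section 9.6 and the 5 in Table 7.

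The cost is wording only. Table 8 does not change. REML intervals are 2–3% (14 df) or 9–11% (9 df) wider than ML with 9 df, and 22–24% or 31–33% wider than ML with a large-sample reference. At the tabled effects 0.30/0.36/0.50, simulated REML power (40,000 trials per ICC) is 96.8/96.8/97.0% with 14 df and 95.5/95.4/95.7% with 9 df. It exceeds the planned 90% because the Section 9.6 model has no intervention main effect and so adjusts for baseline: the variance factor is 1 − 0.5² = 0.75, against 2(1 − 0.5) = 1 in the sample-size formula.
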